## **Missing Data**

Descriptive summary statistics will use all available data. Repeated measures analyses will also use all available data and are expected to provide unbiased estimates under the assumption that data are missing at random (MAR) under the assumed model.

Examination of informative missing data and sensitivity analyses may be performed if necessary and reported in the CSR. Multiple imputation (MI) may be used for sensitivity or secondary analyses.

## **Analysis Populations**

All enrolled patients will be included in the full analysis set (FAS). The FAS will be used for all summaries and analyses unless otherwise specified in the SAP or CSR.

## POTENTIAL RISKS AND BENEFITS

### POTENTIAL BENEFITS

Participants will likely receive no direct benefit from taking part in this research study. However, the knowledge gained regarding liver disease in bariatric surgery patients may benefit public health as a whole. In addition, patients will receive information about their liver health before and after surgery, which may provide some benefit.

### POTENTIAL RISKS

#### **Intravenous Lines/Blood Draws (e.g., Laboratory Samples)**

The placement of IV needles may cause transient pain, vasovagal syncope, and may also result in bruising, bleeding, and/or clotting at the site of needle insertion. The application of direct pressure at the catheterization site will be used to help prevent these symptoms. There is a possibility that a catheter placement would be unsuccessful or need to be removed. If this should occur, another catheter would be placed. It is possible that this may occur more than once during participation in the protocol. Staff who are trained and certified in the SOP will be used.

The total blood collected from each participant will be approximately 545 mL over a 52 week follow up period. This is inclusive of the approximately 90 mL collected at screening. The total blood volume within the first 8 weeks is approximately 280 mL.

#### **Protection Against Risk**

- All venipuncture will be conducted by qualified staff using aseptic techniques to reduce these risks.

#### **Magnetic Resonance Imaging (MRI) and Spectroscopy**

There are no known biological risks associated with MRI and spectroscopy. Some short -term discomfort may be experienced. The short-term risks associated with MRI are minimal, but include heating, loud noises, and claustrophobia. Some of the images require the use a soft rubber-like clip attached to your finger to monitor the heart beat in order to compensate for cardiac motion. There are some people who should not undergo MRI; the contraindication is largely based on the presence of metal objects within a person (i.e., pacemaker, aneurysm clip, metal fragments, etc.).

#### **Protection Against Risk**

- There will be strict safety screening per TRI-MD SOP 030.500.001 to ensure any people with contraindications are excluded from volunteering.
- Optional MRI Acclimatization:

If a participant voices any concerns with tolerability of MRI scans, an acclimatization session may be performed during a screening visit. Participants will undergo an MRI acclimation session where they will be asked to lie in the MRI machine, in a manner similar to that required for MRI procedures in this study, to ensure participant

tolerability. This screening will last up to 5 minutes, and no data will be collected during this acclimation session.

### **Incidental Findings**

There will be no diagnostic analysis associated with any of the MRI sequences used in this protocol. The images obtained at the screening visit will be sent for Radiology review to exclude any obvious medical abnormalities. In the case where an unexpected anatomical or pathological abnormality is reported by the Radiologist, the participant will be excluded from the study and instructed to seek medical attention from their health care provider. On subsequent study visits the images will not be sent for radiology review unless a medical abnormality is apparent on an image. In this case, the images will first be reviewed by an investigator on this protocol. If the abnormality is confirmed by radiology, then the participant will be instructed to seek medical attention from their health care provider. The results of the radiology interpretation will become part of the participant's medical record.

### **FibroScan®**

There are no known risks associated with FibroScan®.

### **Protection Against Risk**

Although there are no known risks, the FibroScan® test will be conducted only by individuals that have been trained and certified by the manufacturer.

### **Quantitative Liver Function Test (HepQuant SHUNT Liver Diagnostic Kit)**

The following includes the known adverse events associated with the use of the HepQuant SHUNT Kit:

1. Risks from the Test Compounds
  - a. Allergic reaction to cholate compounds (theoretical – none yet reported)
  - b. Allergic reaction to human serum albumin (HSA)
  - c. Reactions could include:
    - i. rash
    - ii. having a hard time breathing
    - iii. wheezing when you breathe
    - iv. sudden drop in blood pressure
    - v. swelling around the mouth, throat, or eyes
    - vi. fast pulse
    - vii. sweating
    - viii. severe reactions are very rare but a severe reaction (called anaphylaxis) can lead to profoundly low blood pressure and even death
2. Risks from the Indwelling Catheter
  - a. Pain with placement of catheter
  - b. Thrombosed vein
  - c. Hematoma

## Risks from the Test Compounds

Cholates, labeled with stable (nonradioactive) isotopes, occur naturally and are not known to have any deleterious or adverse effects when given intravenously or orally in the doses used in HepQuant tests. The serum cholate concentrations that are achieved by either the intravenous or oral doses are similar to the serum concentrations of bile acids that occur after the ingestion of a fatty meal. Because cholates are naturally occurring with a pool size in humans of 1 to 5 g, the 20 and 40 mg doses of labeled cholates used in the HepQuant tests are unlikely to be harmful to a fetus. However, the effects of these compounds on the fetus are not definitively known. Possible adverse event associated with the cholate test compounds may include: allergic reaction.

The two cholates used in the HepQuant test for this study are labeled with stable (non-radioactive) forms of carbon and hydrogen that are found in nature and can be measured in blood. These forms of cholate have been used with FDA Investigational New Drug (IND) research studies since 2002, and their use in humans has been monitored since that time. To date, the cholates used in this study have not been associated with any allergic reactions or side effects. However, they are still considered experimental and there may be unknown risks.

**Human serum albumin** is mixed with the  $^{13}\text{C}$ -cholate for IV injection. Some individuals may have a known reaction to serum albumin, and will be excluded from this study. Possible AEs from the HSA may include: allergic reactions.

Rare Hypersensitivity Reactions have been reported to human serum albumin preparations and include anaphylaxis, severe anaphylaxis or anaphylactoid reactions, fever, chills, rash, urticaria, pruritus, angioneurotic edema, and erythema or flushing. Individuals who are hypersensitive to albumin preparations, any ingredient in the formulation, or components of the containers should be excluded from this substudy.

**Risk of Transmissible Diseases in Plasma-derived Preparations.** Because human albumin is prepared from pooled human plasma, there is a potential to pass human viruses (e.g., hepatitis viruses, HIV) to the recipient and may carry a risk of transmitting Creutzfeldt-Jakob disease (CJD) or its variant CJD (vCJD). Through donor plasma screening and specific procedures like pasteurization to eliminate or inactivate any possible causes have reduced, but not entirely eliminated, the risk of transmission of disease causing agents. Risk of transmission of viral disease with plasma-derived human albumin is considered extremely remote. No causes of transmission of HBV, HCV, or HIV have been documented following use of commercially available human albumin. There are no documented cases of CJD or vCJD transmitted through plasma-derived preparations (including plasma-derived human albumin); theoretical risk for transmission of CJD with commercially available human albumin is considered extremely remote.

However, no purification method has been shown to be totally effective in removing the risk of viral infectivity from plasma-derived preparations and because new blood-borne viruses or other disease agents may emerge which may not be removed or inactivated by current manufacturing processes, the risks of human albumin are not entirely known.

## Risks from Indwelling Intravenous Catheter

Placing the indwelling intravenous catheter will cause minor pain and discomfort. With any blood draw, there is a small risk of hematoma and a very small risk of a blood clot (1 in 100) or infection (1 in 1000). HepQuant has performed the HepQuant SHUNT test or the prototypical dual cholate research test on over 500 individuals and most had the test multiple times. There has never been an adverse event (AE) - the risk from the test is very small. Possible adverse event from the placement of an indwelling catheter may include: hematoma at injection site.

### **Special Considerations in Bariatric Populations**

After bariatric surgery, stomach capacity is approximately 30 milliliters. Sugared beverages are not well tolerated after bariatric surgery. It is recommended that 4 meals be consumed per day. Prolonged fasting periods may not be tolerated.

### **Other Considerations**

Beta blockers or angiotensin converting enzyme (ACE) inhibitors could affect the blood flow to the liver, and therefore could affect the flow of the HepQuant SHUNT cholate test compounds into the liver as well. If the flow of blood to the liver was altered by these drugs, it could impact the SHUNT test results. Additionally, because individual participants may take different amounts of these drugs, corrections for the different concentrations and their impact on blood flow to the liver cannot be made. As such, participants who are currently taking either a beta blocker or an ACE inhibitor will be asked to delay taking their normal morning dose the day of their testing and until the 90-minute test is completed. Delaying these medications could cause a temporary elevation in blood pressure but the risk would be minimal, like that of participants that delay doses of medications in everyday life. Participants will therefore be instructed to immediately take their morning dose after the final 90-minute blood draw has been completed. Possible adverse events from delaying taking ACE inhibitor or beta blockers may include minimal change in blood pressure.

### **Protection Against Risk**

- Individuals with a history or suspected hypersensitivity to human serum albumin, or its preparations will be excluded.
- The HepQuant test has not been used on individuals who have undergone bariatric surgery. Therefore, participants will be monitored closely. If there are issues with tolerability, the test will be stopped and no additional tests will be attempted. In addition, the following procedures will be implemented:
  - The total volume of the oral cholate mixture will be 20–30 milliliters.
  - Only artificially sweetened beverages will be used to prepare the cholate solution.
  - Participants will be able to consume clear liquids during the procedure to mitigate the effects of fasting.

### **Liver Biopsy**

In most instances, there are no complications in obtaining a liver biopsy. Performing the biopsy does introduce the risk of bleeding as well as a bile leak from the biopsy site. It is also possible that inadvertent injury can occur to

surrounding organs from the biopsy needle. There are no separate skin incisions or punctures that are required for this procedure and there should be minimal to no added pain from the procedure.

### **Protection Against Risk**

- Bleeding and bile leak risks are minimized by having the biopsy performed under direct visualization of the liver, which allows for the physician to confirm adequate hemostasis and the absence of a bile leak.
- Inadvertent injury to the surrounding organs from the biopsy need are minimized by having the biopsy conducted under direct visualization.
- A pathologist will review the results of the liver biopsy histology and the subsequent results and information will be available to the participant. Significant findings will be reported to the bariatric surgeon. The results from this biopsy will become part of the participant's medical record.

### **Stool Collection**

There are no known risks with collecting stool.

### **Protection Against Risk**

N/A

## **MITIGATION OF RISKS**

Risk monitoring will be performed via a weekly or biweekly individual review of cases by the Principal Investigator, the study physician, and/or research coordinator, including progress or AEs occurring in the following: subject confidentiality, subject recruitment, informed consent process, data quality, and any external factors relevant for the safety of participants throughout the entire study. In addition to these items, the study coordinator has been specifically instructed to make the Primary Investigator aware of all AEs, expected or unexpected that arise during the course of the study. Wound healing after invasive procedures (i.e., IV line placement) will be monitored. Laboratory tests are obtained during the screening visits of the study and any abnormal findings are sufficient to exclude individuals. If an abnormal laboratory value is obtained, the research participant will be referred to their primary care physician for follow-up. If illness or injury occurs during a study procedure, participants will be transported to the Emergency Room if needed.

### **Provisions to Protect the Privacy Interest of Subjects**

Participants will be assigned unique identifiers for study-related records. All precautions will be taken to make sure that only authorized individuals will access subject research records. The collection of sensitive information about subjects will be limited to the minimum necessary to achieve the aims of the research, so that no unneeded sensitive information will be collected.

## EARLY WITHDRAWAL OF SUBJECTS

### Investigator Withdrawal of Subjects

Participation in the study may also be discontinued at any time at the discretion of the Principal Investigator, without participant consent if:

- The Principal Investigator believes it necessary for a participant's health or safety.
- Participant has not followed study instructions.
- Participant is not adherent to the intervention.
- The TRI-MD has stopped the study.
- Administrative reasons require a participant's withdrawal.

Participants will be withdrawn from the study if:

- Participant uses any investigational agent (up to the final study visit).
- Female participant has become pregnant.

### Subject Request for Withdrawal from Study

Participation in this study is voluntary. Participants may decide not to participate in this study or may withdraw from this study at any time without penalty or loss of benefits. If a participant leaves the study before the final regularly scheduled visit, he/she may be asked by the Investigator to make a final visit for 'end-of-study' procedures. This is to ensure there are no safety concerns.

### Data Collection and Follow-up for Withdrawn Subjects

If the study is prematurely terminated, or if a subject requests withdrawal from the study, or if the Principal Investigator withdraws a subject from the study, study data will be maintained in the research database up to the point of withdrawal. This data will be included in subsequent analysis, as keeping these participants in the analysis is essential for study validity.

## ADVERSE EVENT REPORTING

### Adverse Events

An AE is defined as both an expected side effect that is of a serious nature, or an unexpected side effect/event regardless of severity. Each participant is evaluated for AEs at every study visit. Any event that is reported to the study staff and meets the criteria of an AE will be documented as such and graded as to its attribution (unrelated to protocol, or possibly, probably, or definitely related to protocol) and severity (mild, moderate, or severe). Any severe and/or unanticipated AE will be reported to the institutional review board (IRB) according to HRP 801 INVESTIGATOR GUIDANCE: Prompt Reporting Requirements.

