The effect of bariatric surgery on gut microbiome will be assessed through stool sample assays for composition, functionality, and metabolites of microbiota (both stool and circulating). Alterations to the intestinal microbiota have been found to contribute to the pathogenesis of many liver diseases, including NAFLD ([Schnabl 2014](#)). Though the mechanism through which microbiota may negatively or positively influence the onset of NAFLD is not fully understood, it is plausible that investigation of the bacterial dysbiosis that arises in response to bariatric surgery may provide insight to: (1) novel approaches to inhibit pathways that promote disease progression in NAFLD, or (2) identification of non-invasive biomarkers to identify patients at risk for progression to NASH.

The only non-standard of care procedures that will occur during bariatric surgery is a liver biopsy for histology and exploratory analyses. In the post-surgery period, the only non-standard of care activities will be those related to the imaging and sample collection for monitoring of liver health with the specified biomarkers. Research-related procedures occurring before and after surgery are detailed below.

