## **Study Site(s)/Location(s) and Number of Subjects**

AdventHealth Orlando site locations (campus, physician offices, etc.):

- Celebration Health
- Translational Research Institute for Metabolism and Diabetes

Estimated number of participants: 35

The study will enroll 25 participants with NASH for the full study and 10 participants with non-NASH [NAFLD or normal] to serve as controls. The 10 non-NASH participants will have baseline measurements and perioperative biopsies only. In the unlikely instance that biopsy results do not confirm NASH. Those participants who do not have NASH diagnosis will not continue in the post-surgery study visits and may become part of the 10 participants non-NASH group (see Figure 1 below). Additional participants may be recruited if the analysis of the primary end point (12 weeks) reveals larger variability than anticipated.

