The eligible population for enrollment in the full longitudinal study is subjects with biopsy-confirmed NASH. Liver biopsies will be collected at the time of the bariatric surgery procedure; however, in advance of the surgery, screening criteria based on liver imaging assessments will be applied in a sequential manner in effort to help identify eligible subjects.

The MR assessment performed at Screening Visit 2 will serve as the non-invasive qualification of subjects with NASH, which will be defined as those having a liver fat-fraction  $\geq 8\%$  and liver stiffness  $\geq 3.00$  kPa or MRE  $\geq 2.70$  kPa (Chen 2011) with at least one of the following risk factors for NASH: type 2 diabetes, metabolic syndrome, Screening labs or labs drawn within 30 days prior to SV2 (ALT  $\geq 1.5$  times the upper limit of normal, AST to platelet ratio of  $\geq 0.7$ , and/or Fibrosis-4 score suggestive of NASH: Age  $\leq 35$ : score not applicable; Age  $\geq 36$ :  $> 2.67$  (Lin 2011, McPherson 2017). See [Appendix C](#) for description of how the scores are calculated.

The TRI-MD PDFF calculation will be used for determination of eligibility. Only enrolled participants will have their MRI data sent to AMRA and Perspectum for PDFF analysis during the study timepoints indicated in [Appendix A: Schedule of Events](#). During the bariatric surgery procedure, subject inclusion will be confirmed following histological analysis of the liver biopsy. Following bariatric surgery, qualifying subjects will undergo periodic assessments out to 52 weeks post-surgery. In addition, subjects who either (1) do not meet the screening criteria for presumed NASH prior to surgery, or (2) meet the initial screening criteria, but do not meet the biopsy criteria for NASH diagnosis, will be considered for inclusion in a non-NASH cohort whose baseline assessments and perioperative biopsies will serve as control data, but for which no post-surgical longitudinal assessments will be performed.

A summary of the screening criteria for subject eligibility is provided in the decision tree diagram provided in [Figure 1](#).

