## Baseline Visit 2 (BLV2)

This visit will occur within the final 5 days of the standard of care pre-surgery liquid diet. In the rare event that surgery is scheduled without sufficient time to collect BLV1 endpoints, participants can proceed to BLV2 and continue in the study. The following procedures will be performed after an overnight fast:

- AE/concomitant medication review
- body weight measured
- BMI calculated
- single supine vital signs measured
- urine pregnancy test
- blood collection for hemoglobin level
- blood collection for hepatic panel
- blood collection for OWLiver Care, OWLiver, and comprehensive metabolomic panel from OWL Metabolomics
- blood collection for pro-collagen protein fragments panel from Nordic Bioscience
- If BLV1 is not completed, stool collection will occur during this visit or with an at-home kit after the visit
- FibroScan®
- MRI

## Surgery (V3) – Day 1

The following procedures will be performed as part of standard of care for bariatric surgery:

- body weight measured
- BMI calculated
- single supine vital signs measured
- urine pregnancy test
- Roux-en-Y or gastric sleeve will be performed using standard procedures by the bariatric surgeons at Celebration Health.

The following additional research procedures will be performed:

- Two liver biopsies for clinical histology and exploratory endpoints/biobanking

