## APPENDIX A. SCHEDULE OF EVENTS

Description	Screening Visit 1	Screening Visit 2	Baseline Visit 1	Baseline Visit 2	Surgery	Post-Surgery			
Visit Number	SV1	SV2 l	BLV1 m	BLV2	V3	V4	V5	V6	V7
Day a	Varies	Varies	Varies	Varies	1	42 ±7	84 ±7	182 ±14	364 ±14
Physical Exam b	X	X							
Provider time to explain study	X								
Assess participant eligibility	X	X			X				
Informed consent c	X								
Demography c	X								
AE/ConMed review		X	X	X		X	X	X	X
Drug Alcohol Tobacco Screen/AUDIT questionnaire		X							
Height and body weight d	X	X	X	X	X	X	X	X	X
Body Mass Index (BMI)	X	X	X	X	X	X	X	X	X
Vital signs b	X	X	X	X	X	X	X	X	X
Screening Lab assessments (fasting) e		X							
Urine pregnancy test		X	X	X	X	X	X	X	X
Urinalysis		X							
Urine drug screen		X							
HIV, HBV, HCV screen		X							
Hepatic panel			X	X		X	X	X	X
Hemoglobin				X					
Pre-surgery diet f				X					
SoC Bariatric surgery					X				
Liver biopsy g					X				
Blood collections for: OWL Metabolomics Nordic Bioscience			X	X		X	X	X	X
Blood collections for: Biobanking h			X			X	X	X	X
Stool Collection i			X			X	X	X	X
HepQuant SHUNT Dual Cholate Liver Diagnostic Kit j			X			X	X	X	X
IMAGING									
FibroScan®		X		X		X	X	X	X
MRI k		X		X		X	X	X	X

Current Version Date:

24OCT2019

Previous Version Date:

05SEP 2019

Research Study protocol template version date 11/3/2016

IRBNet #: 1000376

Page 43 of 46

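### AE review is promised at every study visit but is not scheduled at surgery, and non-NASH participants have no scheduled AE review after the two research liver biopsies

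*Combined protocol and SAP*

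**What the plan says.** The Adverse Events section of the combined protocol and SAP makes a general promise: "Each participant is evaluated for AEs at every study visit". Appendix A carries this out through the row "AE/ConMed review", marked at SV2, BLV1, BLV2 and V4 to V7, and blank at SV1 and Surgery (V3).

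The procedure list for Surgery (V3) names one additional research procedure: "Two liver biopsies for clinical histology and exploratory endpoints/biobanking". It lists no AE review. Research Design confirms that this is research and not usual care: "The only non-standard of care procedures that will occur during bariatric surgery is a liver biopsy for histology and exploratory analyses". Under Potential Risks, the Liver Biopsy section says: "Performing the biopsy does introduce the risk of bleeding as well as a bile leak from the biopsy site". It also mentions possible injury to nearby organs.

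On cohort size, the section on study sites and number of subjects gives: "Estimated number of participants: 35". These are 25 with NASH and 10 without. For the second group it says: "The 10 non-NASH participants will have baseline measurements and perioperative biopsies only". The text after the exclusion criteria describes the non-NASH cohort as one whose baseline data and biopsies serve as controls, "but for which no post-surgical longitudinal assessments will be performed". Footnote g of Appendix A likewise ends longitudinal assessment for anyone whose biopsy does not show NASH.

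**The concern.** The promise covers every participant at every visit. The schedule does not deliver it at the visit where the main invasive research procedure takes place. For NASH participants this delays the first scheduled review until V4. For non-NASH participants no later study visit exists at which to make up for it. That group includes people who enter as presumed NASH and are reclassified by the biopsy result.

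At stake is the completeness of the safety record for a procedure done only for research. If staff follow the schedule as written, the two cohorts have the same biopsy but very different opportunity for a delayed harm to be recorded. An absence of recorded events among the controls could not then be read as an observed absence.

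**Working it through.** The plan states no figure on this point, so there is none to reproduce. The check sets the visit text beside the schedule and then counts.

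**Step 1. Visit text against Appendix A.**

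| Visit | AE review in visit text | AE mark in Appendix A |
|---|---|---|
| SV1 | yes | blank |
| SV2 | yes | X |
| BLV1 | yes | X |
| BLV2 | yes | X |
| V3 (surgery, biopsies) | no | blank |
| V4, V5, V6, V7 | yes | X |

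Seven of nine visit columns are marked. At V3 the text and the schedule agree with each other and both conflict with the Adverse Events section, so the blank is unlikely to be an artefact of how the table was read. At SV1 the text and the schedule disagree. When SV1 and SV2 are combined, the SV2 mark covers that visit; when they are separate, it does not.

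**Step 2. Scheduled AE reviews after biopsy.**

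- NASH participants: V4, V5, V6 and V7, so 4.
- Non-NASH participants: none, so 0. Their last scheduled review is BLV2, before surgery.
- Planned share with none: 10/35 = 28.6%.

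**Step 3. Delay in the NASH cohort.** Surgery is Day 1 and V4 is Day 42 ± 7, which is study Day 35 to 49. Days since surgery are 35 − 1 = 34 to 49 − 1 = 48.

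**Step 4. Scale, by assumption only.** The documents give no biopsy complication rate. If each participant had probability p of a complication, the chance of at least one among 10 is 1 − (1 − p)^10:

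| Assumed p | Chance of at least one in 10 |
|---|---|
| 0.5% | 4.9% |
| 1% | 9.6% |
| 2% | 18.3% |
| 5% | 40.1% |

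These figures show how likely it is that there would be something to collect. They do not estimate how many events would be missed.

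**Step 5. Do other provisions schedule a contact?**

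- Recording and Notification of Adverse Events requires AE questioning at any contact, but no contact after biopsy is planned for the non-NASH cohort.
- The Adverse Events section also covers events reported to staff. That is passive.
- Mitigation of Risks sets a weekly or biweekly case review by staff. It does not require contact with the participant.
- Subject Request for Withdrawal from Study allows a closing visit for those who leave before their last scheduled visit. For non-NASH participants the last scheduled visit is surgery itself.
- Safety Monitoring assigns AE documentation to the coordinator, the investigator and institute staff. The surgeon is not named, and surgery takes place at the other location.

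**The case against.** A reader might infer that biopsy harms in the non-NASH cohort will go uncollected, that these participants have no later contact with anyone, or that the cohort will show zero harms by design. The documents do not support any of these. An event reported to staff must be documented, and any contact triggers AE questioning. Participants may receive biopsy results and are offered a meeting to review laboratory and other standard clinical results, and Research Design says that all participants have the usual post-surgery medical visits. Events could come to light by any of these routes.

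Nor is the operating room unobserved. Under the biopsy risk protections, the needle is used under direct vision, so the surgeon can check for bleeding and bile leak at the time. This largely answers the worry about immediate events. What stands is the delayed event, and the missing statement of how surgical findings reach the AE form.

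Two further objections are fair. First, a mark at V3 captures only same-day events, so it cannot close the gap without a later check. Second, the protocol counts an expected side effect as an AE only if it is serious, so a minor bleed might not be recorded even when asked about. This limits what any review yields but does not remove the need for one.

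It can also be said that nothing here touches an endpoint. That is correct: Table 1 contains no safety objective. For the same reason, a confidence limit on 0 events in 10 would add nothing; better collection would leave it unchanged.

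**Conclusion.** The point holds as an internal contradiction and a gap in scheduled safety collection. The Adverse Events section is contradicted at V3 by both the visit list and Appendix A, and Appendix A also departs from the SV1 text. Scheduled post-biopsy AE reviews number four for NASH participants, starting 34 to 48 days after surgery, and none for the planned 10 of 35 non-NASH participants. For that cohort, capture of delayed biopsy harms rests on spontaneous report or incidental contact.

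This rests on reading V3 as a study visit, as its number and its column in Appendix A indicate, and on the planned cohort sizes. The non-NASH number may differ once biopsy results are known. It also assumes that no unpublished site procedure supplies the missing contact. The sample size and primary analysis are unaffected, so this should be corrected as a matter of safety recording and does not threaten the study's conclusions on its imaging endpoints.

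**What to change.** 1. Reconcile the SV1 text, the V3 procedure list and Appendix A with the Adverse Events section: mark AE review at SV1 and V3 in the schedule, and add it to the V3 list.
2. For every participant who stops at biopsy, record post-biopsy AEs once before close-out, from the standard-of-care post-operative record or by one phone contact. State who does this and when.

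The cost is two schedule marks, one added line, and one chart review or call for about 10 people. No procedure is added and clinical care does not change. The only downside is minor coordinator time.
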